8.2 Classification of Adverse Events by Severity

All toxicities/adverse events will be graded according to the following definitions to code the intensity of the event.

Mild: Usually transient, requiring no special treatment, and does not interfere with the subject's daily activities.

Moderate: Traditionally introduces a low level of inconvenience or concern to the subject and may interfere with daily activities, but are usually relieved by simple therapeutic measures.

Severe: Causes an interruption of the subject's usual daily activity and traditionally required systemic drug therapy or other treatment.

Note: If the intensity of an adverse event changes, the event will be reentered as a separate event.

There is a distinction between the severity and the seriousness of an adverse event. Severity is a measurement of intensity; thus, a severe reaction is not necessarily a serious adverse event. For example, a headache may be severe in intensity, but would not be serious unless it met one of the criteria for serious adverse events listed previously.

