Possible contamination of IVIG with infectious agents like viruses and prions always exists. However, viral inactivation steps, caprylation, and nanofiltration aid in the safety profile of IVIG.

2 Study Objectives

The main objective of this study is to establish whether patients with Dry Eye Disease are able to safely tolerate receiving Intravenous Immunoglobulin (IVIG) eye drops two times a day for eight weeks (primary 'safety and tolerability' objective). The exploratory objective is to investigate the preliminary efficacy of the use of IVIG eye drops in treating Dry Eye Disease (exploratory efficacy objective) to estimate the effectiveness of the trial intervention and collecting data to inform the design of a future definitive trial.

3 Study Design

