3.1 General Design

This will be a Randomized controlled trial, in which a total of 28 subjects will be enrolled at 1 clinical site. Subjects will be randomly assigned to one of two groups (#1, #2), with 14 subjects per group. One group will be given placebo (Normal saline eye drops) and the other group will be given eye drops containing the study drug (IVIG).

Patients with established Dry Eye Disease will be approached by a member of the research staff to determine if he/ she might be interested in participating in a research study. If the subject is interested, the research staff member will describe the study. If the subject is willing to enter the study, the study will be discussed and the subject will be asked to sign the informed consent form. Consent will be obtained prior to screening to determine eligibility. Screening procedures include documentation of Dry Eye Disease. Eligible subjects will be enrolled in the study.

All enrolled subjects will receive their first dose of test medication (placebo/ study drug) on study Day 1 in the doctor's office, and after completion of the study assessments, will have the topical eye drops dispensed for self-administration. See Section 5.4 *Preparation and Administration of Study Drug* for details.

Subjects will be provided with diaries to record the time of each dose and will also be asked to record any adverse symptoms. In addition, they will be asked to make a note of any missed doses together with the reason for the omission. Subjects will return at 4 weeks for further study assessments,

thereafter at 8 weeks (the last day of treatment), and again at 10 weeks after two weeks of no treatment with study drug for the final study assessments.

There is no primary efficacy endpoint in this study. Instead several exploratory efficacy endpoints will be assessed.

The primary tolerability endpoint is the change in the test substance tolerance between Day 1 (post-dose) and 8 weeks (56 days).

[figure not shown]

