3.5 Safety Endpoints

Safety assessments include Vital Signs, recording of all complications and adverse events, as well as ophthalmic exam findings. All ocular and non-ocular adverse events will be assessed for severity and relationship to the investigational product.

In addition to the primary tolerability endpoint (Section 2.2), the following safety endpoints will be assessed:

- The proportion of screened subjects who are successfully recruited in the study (i.e., recruitment rate)
- The proportion of eligible subjects at Day 56 who successfully complete (i.e., retention rate, (non)compliance or adherence rate) a full eight weeks (i.e., 56 days) of therapy with topical administration two times per day (BID).
- All reported adverse events, classified by frequency, severity, and relatedness, from baseline (Day 1) through the last study visit (Day 70).
- Clinically significant changes in vital signs or ophthalmic examination from baseline.

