7.2 Statistical Methods

Based on the classification of reasons for conducting pilot studies by Thabane et al, in this pilot study we will assess the following: (i) Process– recruitment rate, retention rate, (non)compliance or adherence rate; and (ii) Scientific– safety (adverse event/SAE rate), tolerability, and efficacy, including reduction in clinical signs and symptoms (OSDI, Corneal staining, Redness etc as detailed in section 3.4) and treatment effect size. We will calculate the observed rate with 95% confidence interval for each rate by treatment group. Other descriptive statistics, including median with interquartile or mean with standard deviation for continuous variables and frequency with percentage for categorical variables will be reported as well. To estimate the preliminary efficacy under the scientific category, one eye (target eye) will be selected at screening visit as follows: (i) if only 1 eye meets inclusion criteria, this eye is used; (ii) if both eyes meet inclusion criteria, the eye with the higher corneal stain score is used; (iii) if both eyes have the same corneal stain score, then the one with the lower Schirmer I score is used; (iv) if both eyes have same scores, the right eye is used. Secondary analyses will be performed for the non-target eye as well. Due to the nature of this feasibility study, any efficacy statistical tests and adjusted analyses will not be conducted. Detailed data validation will examine completeness, existence and accuracy of collected data to assess data quality and identify missing and conflicting data. Statistical analysis will be performed on an intention-to-treat basis i.e., inclusion of all patients randomly assigned, regardless of adherence, actual treatment received, and subsequent withdrawal of treatment and/or deviation from the protocol and per-protocol (i.e., inclusion of those who completed the treatment as planned) and will be reported according to 2010 CONSORT guidelines. All statistical analyses will be completed using SPSS Statistics V.22.0.31

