All AEs and SAEs whether volunteered by the subject, discovered by study personnel during questioning, or detected through physical examination, laboratory test, or other means will be reported appropriately. For each adverse event, the following information will be recorded on the subject's Case Report Form(s): onset date, end date or continues, intensity, duration, relationship to test patch, action taken, and outcome. If a subject experiences a serious adverse event (SAE), study staff may discontinue the subject from study participation. The study staff must notify the IRB within 24 hours of receipt of the information. The study staff will instruct the subject to notify the research facility should any adverse event occur within 7 days of study completion. (For definitions of an AE and SAE, see below). Subjects who withdraw due to an adverse event may be replaced.

- **Serious Adverse Event:** An AE should be classified as an SAE if the following criteria are met:
 1. It results in death (i.e., the AE actually causes or leads to death.).
 2. It is life-threatening (i.e., the AE, in the view of the investigator, places the subject at immediate risk of death. It does not include an AE that, had it occurred in a more severe form, might have caused death.).
 3. It requires or prolongs inpatient hospitalization.
 4. It results in persistent or significant disability/incapacity (i.e., the AE results in substantial disruption of the subject's ability to conduct normal life functions).

5. It results in a congenital anomaly/ birth defect in a neonate/infant born to a mother exposed to the investigational medicinal product (IMP).
6. It is considered a significant medical event by the investigator based on medical judgement (e.g., my jeopardize the subject or may requires medical or surgical intervention to prevent any of the occurrences listed above.

To ensure consistency of AE and SAE causality assessments, the following general guideline will be applied:

Yes

There is a plausible temporal relationship between the onset of the AE and administration of the IVIG, and the AE cannot be readily explained by the subject's clinical state, intercurrent illness, or concomitant therapies; and/or the AE follows a known pattern of response to the IVIG; and/or the AE abates or resolves upon discontinuation of the IVIG or dose reduction and, if applicable, reappears upon re-challenge

No

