8.5 Adverse Event Reporting

All subjects who have been exposed to study drug will be evaluated for adverse events. Adverse events will be recorded starting after the first dose of study drug and continuing until the end of the study. All adverse events will be evaluated beginning with onset, and evaluation will continue until resolution is noted, or until the Investigator determines that the subject's condition is stable, whichever is earlier. The Investigator will take all appropriate and necessary therapeutic measures required for resolution of the adverse event. Any medication necessary for the treatment of an adverse event must be recorded on the concomitant medication case report form. If more than one distinct adverse event occurs, each event should be recorded separately. Procedures such as surgery should not be recorded as adverse events. However, the medical condition for which the procedure was performed should be reported if it meets the definition of adverse event as described previously.

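### An adverse event is re-entered as separate at each change of intensity and the AE rate has no counting unit, so event-level frequency and severity tables would be inflated

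*Combined protocol and SAP*

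**What the plan says.** Section 8.2 grades AEs as mild, moderate or severe and adds a note: "If the intensity of an adverse event changes, the event will be reentered as a separate event".

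Section 8.5 sets a related rule: "If more than one distinct adverse event occurs, each event should be recorded separately". It also has each event evaluated from its onset until it resolves or is judged stable.

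Section 8.1 lists what is recorded for each AE: "onset date, end date or continues, intensity, duration, relationship to test patch, action taken, and outcome". No field in that list ties one entry to another.

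On reporting, Section 3.5 makes this a safety endpoint: "All reported adverse events, classified by frequency, severity, and relatedness, from baseline (Day 1) through the last study visit (Day 70"). Section 7.2 names "safety (adverse event/SAE rate), tolerability, and efficacy" among the scientific outcomes and continues: "We will calculate the observed rate with 95% confidence interval for each rate by treatment group". Neither 7.2 nor 7.3 states the numerator or denominator of the AE rate, the type of interval, or how repeated entries from one subject are handled.

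On status, Section 2 gives the study a "primary 'safety and tolerability' objective", but the named endpoint in Section 3.1 is different: "The primary tolerability endpoint is the change in the test substance tolerance between Day 1 (post-dose) and 8 weeks (56 days"). Section 3.5 lists AEs as additional to it.

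**The concern.** The note in 8.2 makes the grade, not the episode, the unit of entry, and it calls each new entry a separate event. Section 3.5 tabulates all reported events. Nothing in between brings the entries of one episode back together, takes the highest grade, or counts a subject once. An analyst who follows the text literally therefore counts an episode as many times as its grade was assigned.

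Two outputs are exposed. The first is event frequency, with any event rate and interval built on it. The second is the severity table, where one episode contributes to more than one grade. Section 1.7 says IVIG has not been given as eye drops before, and Section 2 wants the data to inform a later definitive trial. With 12 to 14 subjects per arm, a few fluctuating episodes could dominate an event table.

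**Working it through.** **What the plan's figures provide.** The documents state no AE rate, so there is none to reproduce. The figure that supplies the denominator is the recruitment target in Section 7.1: 12 per arm with 10% attrition gives 12 / 0.9 = 13.3, rounded up to 14 per arm, or 28 in total. This agrees with the plan.

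**Assumed inputs.** In one arm, 4 subjects have one AE episode each. Each episode produces k entries: k = 1 with no grade change, k = 2 with one change, k = 3 for mild, moderate, mild. Both the 4 and the k are assumptions.

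**Formulas.** With x entries in n subjects, the event rate is x / n. Its exact Poisson 95% limits are χ²(0.025; 2x) / (2n) and χ²(0.975; 2x + 2) / (2n). The subject-level rate is subjects with at least one AE divided by n, with a Clopper-Pearson interval.

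**Results for n = 12.**

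| Entries per episode | Entries | Entries per subject (95% CI) | Upper/lower limit | Subjects with at least one AE |
|---|---|---|---|---|
| 1 | 4 | 0.33 (0.09 to 0.85) | 9.4 | 4/12 = 33% (9.9% to 65.1%) |
| 2 | 8 | 0.67 (0.29 to 1.31) | 4.6 | unchanged |
| 3 | 12 | 1.00 (0.52 to 1.75) | 3.4 | unchanged |

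The event rate doubles or triples. The interval also becomes too tight relative to its estimate (upper/lower ratio 3.4 instead of 9.4), because repeat entries from one subject are treated as independent events.

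**Range.** With three entries per episode and n = 12, 2 episodes move the rate from 0.17 to 0.50 and 6 episodes move it from 0.50 to 1.50. In the last case there are 18 entries in 12 subjects, so the rate cannot be a proportion of subjects. With n = 14, 4 episodes move it from 0.29 to 0.86, while the subject-level figure stays at 4/14 = 29% (8.4% to 58.1%).

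**Severity table.** Four mild-moderate-mild episodes counted once at maximum intensity give 4 moderate events. Counted by entry they give 8 mild and 4 moderate, so the moderate share falls from 4/4 = 100% to 4/12 = 33%. Re-entry raises the number of events and lowers their apparent severity at the same time.

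**The case against.** The best answer is that 8.2 is a recording rule, not a counting rule. Section 7.2 lists the AE rate alongside recruitment, retention and adherence, and 3.5 defines those as proportions of subjects. A subject-level AE rate is an equally natural reading, and re-entry leaves it untouched. This stands for the 7.2 rate. It does not settle the 3.5 endpoint, which speaks of all reported events by frequency and severity.

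It can also be said that the data are recoverable: entries carry dates and intensity, and in 24 to 28 subjects consecutive entries could be joined by hand. That is probably true, but no link field is listed and no rule tells the analyst to do it. Nor do 8.2 and 8.5 strictly conflict, since one can be read as a special case added to the other.

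A reader might infer more than the documents support:

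- That the primary safety result is inflated. AEs serve the primary objective, but the named primary endpoint is the VAS change. No efficacy tests are planned and there is no formal sample size calculation, so no error rate or power figure is affected.
- That durations are shortened because earlier entries close on the day the grade changes. No section says how the earlier entry is closed, and the form allows an event to be marked as continuing.
- That 12 entries in 14 subjects is an 86% AE rate. Entries are not binomial trials on subjects, and the plan proposes no such calculation.
- That the comparison of arms is biased. This would need intensity to change more often in one arm, which nothing shows.

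**Conclusion.** The point holds for event-level results. Read as written, 8.2 together with 3.5 counts one fluctuating episode two or three times and spreads it over severity grades, and 7.2 leaves the AE/SAE rate undefined. In the illustration, 4 episodes in 12 subjects become 12 entries, and 0.33 per subject becomes 1.00. That size rests on assumed counts and on every episode changing grade twice; with fewer changes the inflation is smaller, and with none it is zero. The percentage of subjects with at least one AE is unaffected. This is a modest defect in a descriptive safety endpoint. It is worth correcting because it lies in a stated rule and costs almost nothing to repair.

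**What to change.** - **Section 7.2:** define the AE/SAE rate as dosed subjects with at least one event divided by dosed subjects, by arm, with an exact (Clopper-Pearson) 95% interval. The dosed denominator matches 8.5, which evaluates everyone exposed to study drug for AEs.
- **Section 8.2:** replace the note so that a change of intensity is recorded as a linked, dated entry of the same event.
- **Section 3.5:** state that each event is counted once, at its maximum intensity, in the frequency and severity tables.

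The intensity history that re-entry was presumably meant to keep is preserved. The cost is one sentence in each of the three sections and a link field or similar small change to the AE case report form. No new visits or data are needed. It is best settled before entries accumulate without links.

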8.3 Action(s) Taken

One or more of the following will be recorded by the Investigator for each adverse event:

- No action taken
- Discontinued study drug (Subject withdrawn due to this adverse event)
- Administered therapy
- Hospitalized subject (due to this adverse event)
- Other (specify) - includes tests, labs confirming reaction

8.4 Outcome

The status of each adverse event will be recorded as follows, if applicable: SAE: Indicates that the adverse event met the criteria of a serious adverse event (SAE) and the SAE was reported to the IRB. Caused Withdrawal: Indicates that the adverse event caused the subject's withdrawal from the study.

8.5 Adverse Event Reporting

All subjects who have been exposed to study drug will be evaluated for adverse events. Adverse events will be recorded starting after the first dose of study drug and continuing until the end of the study. All adverse events will be evaluated beginning with onset, and evaluation will continue until resolution is noted, or until the Investigator determines that the subject's condition is stable, whichever is earlier. The Investigator will take all appropriate and necessary therapeutic measures required for resolution of the adverse event. Any medication necessary for the treatment of an adverse event must be recorded on the concomitant medication case report form. If more than one distinct adverse event occurs, each event should be recorded separately. Procedures such as surgery should not be recorded as adverse events. However, the medical condition for which the procedure was performed should be reported if it meets the definition of adverse event as described previously.

8.6 Serious Adverse Event Reporting

All Serious Adverse Events (SAE) that occur during the course of the study, including death, which are unanticipated require reporting to the IRB within **5 business** days of the investigator becoming aware. Serious adverse events will be recorded starting after first dose of study drug and continuing until the end of the study. The minimum information to be provided includes:

1. Protocol Number
2. Initial reporter
3. Subject identification
4. Nature and date of the event/effect
5. Country of the event/effect
6. Severity of the event/effect
7. Reporting criteria
8. Narrative description of the event/effect
9. Outcome if known
10. Causal relationship to the investigational product
11. Additional and follow-up information as requested by the medical monitor.

Events requiring reporting to the IRB within **15 business days** of the investigator becoming aware include:

1. Local adverse events or problems that are unanticipated and, while not meeting the criteria of serious, indicate research is associated with a greater risk of harm to participants or others than previously known.
2. New information indicating an unexpected change to the risks or benefits of the research (i.e., an unanticipated problem).
3. Administrative hold by investigator, regulatory authorities or other entities.

8.7 In Case of an Emergency

In medical emergencies, the Investigator should use medical judgment and remove the subject from immediate hazard. The IRB should be notified as to the type of emergency and the course of action taken. The CRF and the source document for the subject must describe the departure from the protocol and state the reason.

8.8 Data Safety Management Plan

The study protocol will be reviewed and approved by the UIC IRB. Adverse events and compliance will be monitored. Research staff will be trained on the protocol requirements and data collection methods before completing study related procedures. Privacy, coding, storage: Research staff will be trained on the protocol requirements and data collection methods before completing study related procedures. Random study ID numbers will be assigned to study subjects. A master code list will link the subject MRN to the study ID number. The data collected will be stored on PI's desktop in a HIPPA compliant encrypted folder at the Ear and Eye Infirmary and Lions Eye Research building. The data collected, master code list will be accessible only to the PI and the research team involved in this project. The desktops will be password protected as well.

All Serious Adverse Events (SAE) that occur during the course of the study, and possibly related to the study intervention, including death, which are unanticipated will be reported to the IRB within 5 business days of the investigator becoming aware. A copy of the report will be sent to the FDA.

Events requiring reporting to the IRB within 15 business days of the investigator becoming aware include:

- Local adverse events or problems that are unanticipated and, while not meeting the criteria of serious, indicate research is associated with a greater risk of harm to participants or others than previously known.
- New information indicating an unexpected change to the risks or benefits of the research (i.e., an unanticipated problem).

A copy of this report will be sent to the FDA.

The minimum information to be provided includes:

1. Protocol Number
2. Initial reporter
3. Subject identification
4. Nature and date of the event/effect
5. Country of the event/effect
6. Severity of the event/effect

7. Reporting criteria
8. Narrative description of the event/effect
9. Outcome if known
10. Causal relationship to the investigational product
11. Additional and follow-up information as requested by the medical monitor.

8.9 Study Oversight

The Study PI has primary oversight responsibility for this study. [name] is a board certified Ophthalmologist with an active practice in the area of Dry Eye Disease, including those with Meibomian Gland Disease. He routinely takes care of patients with severe ocular surface disease. He's also the director of Dry Eye service at UIC. Therefore, he's well qualified to recognize the symptoms and clinical signs of an adverse event. [name] has been the PI of past and active IRB approved clinical studies and has monitored data related to those studies. Therefore, he has experience in data and safety monitoring.

The Principal Investigator and his research team are responsible for identifying adverse events. Safety monitoring will include careful assessment and appropriate reporting of adverse events. Subjects will be reminded to inform the study staff of any adverse effects that they have experienced or are experiencing after the first administration of study drug. Subjects will be provided with diaries to record at home the time of each dose and any adverse symptoms. All reports of adverse events during the study will be recorded on an Adverse Event Case Report Form (CRF). In addition, subjects will be asked to make a note of any missed doses together with the reason for the omission. A member of the research staff will review diary entries with the subject at each study visit. Subjects will be asked to bring back the left-over drug at each study visit. The amount of drug remaining in the used vial will also give an estimate of the compliance.

9 Confidentiality

Information about study subjects will be kept confidential and managed according to the requirements of the Health Insurance Portability and Accountability Act of 1996 (HIPAA). Those regulations require a signed subject authorization informing the subject of the following:

- What protected health information (PHI) will be collected from subjects in this study
- Who will have access to that information and why
- Who will use or disclose that information
- The rights of a research subject to revoke their authorization for use of their PHI.

In the event that a subject revokes authorization to collect or use PHI, the investigator, by regulation, retains the ability to use all information collected prior to the revocation of subject authorization. For subjects that have revoked authorization to collect or use PHI, attempts should be made to obtain permission to collect at least vital status (i.e. that the subject is alive) at the end of their scheduled study period.

10 Source Documents

Source data is all information, original records of clinical findings, observations, or other activities in a clinical trial necessary for the reconstruction and evaluation of the trial. Source data are contained in source documents. Examples of these original documents, and data records include: hospital records, clinical and office charts, laboratory notes, memoranda, subjects' diaries or evaluation checklists, pharmacy dispensing records, recorded data from automated instruments, copies or transcriptions

certified after verification as being accurate and complete, microfiches, photographic negatives, microfilm or magnetic media, x-rays, subject files, and records kept at the pharmacy, at the laboratories, and at medico-technical departments involved in the clinical trial.

